7. CONCOMITANT MEDICATIONS

Disallowed medications include:

- Antihistamines (including sleep-aids containing an antihistamine) at least 7 days prior to Visit 1 (Day -14 to Day 0) and through Day 98.
- Topical cyclosporine or lifitegrast or omega-3s within 14 days prior to Visit 1 (Day -14 to Day 0) and through Day 84. Supplements containing omega-3 are allowed if the subject has been taking said supplement for at least 3 months prior to Screening. Subjects are not allowed to begin taking supplements containing omega-3 during the study.
- Corticosteroids or mast cell stabilizers (including ocular): 14 days prior to Visit 1 (Day -14 to Day 0) and through Day 84.
- Depot-corticosteroids in either eye at least 45 days prior to the first dose of study drug (Day 0) and through Day 84.
- All other topical ophthalmic preparations (including artificial tear substitutes) at least 72 hours prior to Visit 2 (Day 0) through Visit 7 (Day 98).
- Use of any topical medication and/or antibiotics for the treatment of blepharitis or meibomian gland disease in either eye within 14 days prior to Visit 2 (Day 0) through Visit 7 (Day 98).

- Introduction of any new, nonsteroidal anti-inflammatory drugs (NSAIDs) including but not limited to topical, systemic (including sleep-aids containing NSAIDs), inhaled, or irrigation solution within 7 days prior to the first dose of study drug is not permitted. Subjects who are on stable dose of NSAIDs (stable for at least 4 weeks prior to the first dose of study drug) are eligible for participation and should remain on a stable dose throughout the duration of the study (i.e., through Day 98). If a subject takes an NSAID as needed (PRN) during the conduct of the study, that is permitted but subjects should be requested not to take an NSAID within the 24 hours prior to a scheduled study visit.
- Triamcinolone in either eye at least 90 days prior to the first dose of study drug (Day 0) and through Day 84.
- Inhaled, ingested, sublingual, transdermal or topical products containing marijuana, tetrahydrocannabinol (THC) or cannabidiol (CBD) at least 7 days prior to the first dose of study drug (Day 0) through Day 84.
- Systemic pain relievers, analgesics (e.g., pregabalin, gabapentin, opioids) 14 days prior to the first dose of study drug (Day 0) through Day 98.
- Any supplement, prescribed medication or over-the-counter product that the investigator feels may interfere with the study parameters, including homeopathic remedies, analgesics, and pain medication through Day 84.
- Oral doxycycline within 6 months of first dose of study drug (Day 0) through Day 84.
- Diuretics: Within 28 days prior to Visit 1 (Day -14 to Day -1) through Day 84.

Prior medications (both prescription and non-prescription [including over the counter medicine, vitamins, supplements, and herbal supplements]) taken within 3 months before the screening visit will be recorded in the source documents and entered on the appropriate electronic case report form (eCRF). All concomitant medications taken throughout the course of the study, including any medications required to treat AEs or concomitant illnesses and any changes in concurrent medications, will also be recorded in the source documents and entered on the appropriate eCRF. Concomitant medications used for ocular exams, including but not limited to Fluress®, proparacaine, benoxinate or fluorescein, will not be collected.

8. CLINICAL ASSESSMENTS/EXAMINATION PROCEDURES

Subject Completed Assessments:

UNC DEMS Questionnaire: The UNC DEMS will be completed by subjects at Visit 1 (Screening; Day -14 to Day 0) and only at Visit 2 (Day 0) if Visit 2 is >5 days following Visit 1. The UNC DEMS will also be completed by subjects at Visit 3 (Day 7) through Visit 7 (Day 98).

Dosing Diary with Drop Comfort Questionnaire: Subjects will be given a Dosing Diary with Drop Comfort Questionnaire to record study drug dose instillation dates and times for each dose, as well as to record their responses to the Drop Comfort Questionnaire every 7 days during the dosing period (Day 0 to Day 83).

Investigator Assessments:

Best-Corrected Visual Acuity (BCVA): BCVA will be performed in both eyes at Visit 1 (Screening; Day -14 to Day 0) and only at Visit 2 (Day 0) [prior to randomization] in both eyes if Visit 2 is >5 days following Visit 1. BCVA will also be performed in treated eyes at Visit 3 (Day 7) through Visit 7 (Day 98). Log of the minimum angle of resolution [logMAR] score using ETDRS [Early Treatment Diabetic Retinopathy Study] chart will be used to measure BCVA. Performing a pinhole test is allowed as long as its use remains consistent for the same subject throughout all study visits.

Biomicroscopy: Slit lamp biomicroscopy will be performed to observe the overall health of the eye, including the lid/lashes, conjunctiva, cornea, anterior chamber, iris, and lens. This will be performed in both eyes at Visit 1 (Screening; Day -14 to Day 0) and only at Visit 2 (Day 0) [prior to randomization] if Visit 2 is >5 days following Visit 1. Slit lamp biomicroscopy will also be performed in treated eyes at Visit 3 (Day 7) through Visit 7 (Day 98).

Ophthalmoscopy: An undilated ophthalmoscopy exam will be performed in both eyes at Visit 1 (Screening; Day -14 to Day 0) and in treated eyes at Visit 7 (Day 98).

Intraocular Pressure (IOP): IOP will be measured in both eyes at Visit 1 (Screening; Day -14 to Day 0) and only at Visit 2 (Day 0) [prior to randomization] if Visit 2 is >5 days following Visit 1. IOP will also be measured in treated eyes at Visit 3 (Day 7) through Visit 7 (Day 98).

Conjunctival Hyperemia Assessment: Conjunctival hyperemia will be assessed in both eyes at Visit 1 (Screening; Day -14 to Day 0) and only at Visit 2 (Day 0) [prior to randomization] if Visit 2 is >5 days following Visit 1. Conjunctival hyperemia will also be assessed in the treated eye(s) at Visit 3 (Day 7) through Visit 7 (Day 98).

Tear Break-up Time (TBUT): TBUT will be conducted in both eyes at Visit 1 (Screening; Day -14 to Day 0) and only at Visit 2 (Day 0) [prior to randomization] if Visit 2 is >5 days following Visit 1. TBUT will also be measured in the treated eye(s) at Visit 3 (Day 7) through Visit 7 (Day 98).

Fluorescein Corneal Staining: Fluorescein corneal staining will be conducted in both eyes at Visit 1 (Screening; Day -14 to Day 0) and only at Visit 2 (Day 0) if Visit 2 is >5 days following Visit 1. Fluorescein corneal staining will also be measured in the treated eye(s) at Visit 3 (Day 7) through Visit 7 (Day 98).

Conjunctival Staining: Conjunctival staining using fluorescein dye will be conducted in both eyes at Visit 1 (Screening; Day -14 to Day 0) and only at Visit 2 (Day 0) if Visit 2 is >5 days following Visit 1. Conjunctival staining will also be measured in the treated eye(s) at Visit 3 (Day 7) through Visit 7 (Day 98).

Schirmer Tear Test: Schirmer tear tests will be conducted with anesthesia in both eyes at Visit 1 (Screening; Day -14 to Day 0) and only at Visit 2 (Day 0) if Visit 2 is >5 days following Visit 1. Schirmer tear tests (with anesthesia) will also be conducted in the treated eye(s) at Visit 3 (Day 7) through Visit 7 (Day 98) to assess aqueous production.

Adverse Events and Concomitant Medications: At each study visit, subjects will be queried for new adverse events and, if applicable, previously unresolved adverse events. Also, concomitant medications will be documented.

Diary: At Visit 2 through Visit 6 (Day 0 through Day 84), subjects' Dosing Diaries will be reviewed and compliance with study drug dosing and completion of the Drop Comfort Questionnaire will be evaluated.

Biomicroscopy and ophthalmoscopy study examinations should be performed by the same board-certified ophthalmologist or a board-certified or state licensed optometrist (that would allow them legally to diagnose and treat patients independently) from visit to visit. All other ratings and procedures should be performed by the same examiner from visit to visit whenever possible.

9. ADVERSE EVENTS

Throughout the course of the study, the investigator must remain alert to possible adverse events or untoward findings. If adverse events occur, the first concern will be the safety of the subject. Appropriate medical intervention will be provided by the investigator.

Adverse Event (AE) Definition: An AE is any untoward medical occurrence associated with the use of a study drug in a clinical investigation subject, whether or not considered related to the study drug.

Adverse Event Reporting Period: The AE reporting period for this trial begins upon signing the ICF and ends at the completion of the subjects' final study visit exam. All AEs reported by the subject during the course of the study, or elicited by questions from the investigator, or noted as a result of procedures carried out on the subject, during the AE-reporting period must be recorded by site staff in the source documents and on the AE eCRF, whether or not the event is considered related to the study drug. In addition, any known untoward event that occurs subsequent to the AE reporting period that the investigator assesses as related to the study drug should also be reported as an AE.

Serious Adverse Event (SAE) Definition: A serious adverse event (SAE) or reaction is any untoward medical occurrence that at any dose:

- Results in death
- Is immediately life-threatening or immediately sight-threatening in a treated eye(s)
- Requires inpatient hospitalization or prolongation of existing hospitalization
- Results in persistent or significant incapacity or substantial disruption of the ability to conduct normal life functions
- Is a congenital anomaly/birth defect
- Is an important medical event that may jeopardize the subject or may require medical intervention to prevent one of the outcomes listed above

SAE Reporting: SAEs must be immediately reported (within 24 hours of awareness of the event) to designated contract research organization (CRO) and will be clearly documented in the source documents and on the appropriate AE eCRF and SAE Report Form. The investigator must also notify the IRB of any SAEs, according to the IRB's guidelines.

Pre-existing Conditions: In this trial, a pre-existing condition (i.e., a disorder present before the AE-reporting period started and noted on the Systemic and/or Ocular Medical History Forms) should not be reported as an AE unless the condition worsens, or episodes increase in frequency or severity during the AE-reporting period.

BCVA: A worsening of 3 lines or more in log of the minimum angle of resolution (logMAR) score in the study eye from baseline or any prior visit should be captured in the source documents and on the appropriate eCRF as an AE.

IOP: An increase from baseline or any prior study visit of 10 mmHg in IOP in the study eye should be captured in the source documents and on the appropriate eCRF as an AE. An IOP of 30 mmHg or higher will be reported as an SAE.

Biomicroscopy: Slit lamp biomicroscopy will be performed to observe the overall health of the eye, including the lid/lashes, conjunctiva, cornea, anterior chamber, iris, and lens. Any biomicroscopy observations noted prior to Screening (Visit 1) should be recorded as ocular medical history. Any treatment-emergent findings (i.e., findings that were not present prior to treatment or a worsening relative to the pretreatment baseline) should be recorded as an AE.

Ophthalmoscopy: A new finding or a significant worsening (2 units or more) from baseline should be recorded as an AE.

AE Considerations: Additional exams may be scheduled as necessary to ensure the safety of the subjects during the study period. Subjects discontinued due to an AE should be seen for post-study follow-up visits, as needed. Adverse events considered related to study drug that have not resolved or stabilized by the final study visit will be followed during post-study follow-up visits at the discretion of the investigator until the incident has resolved or stabilized and will be documented in the source documents and AE eCRF. Where appropriate, additional written reports and documentation will be provided. Adverse events considered not related to study drug that have not resolved or stabilized by the final study visit will be noted as ongoing in the eCRF, followed at the discretion of the investigator, and recorded in the source documents.

Pregnancy: Although pregnancy is not considered an AE, any complication related to pregnancy would be considered an AE and recorded in the source documents and, if applicable, on the AE eCRF. If an SAE is associated with the pregnancy, the SAE should be reported on the SAE Report Form.

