Subjects will be randomly assigned to receive treatment twice daily (BID) for 84 days (Days 0 to 83). Subjects will receive instructions for dosing at home and for completing a dosing diary during the study dosing period (Visit 2 [Day 0] to Visit 6 [Day 84]).

Subjects (or their caregivers) will be instructed to store the study drug at room temperature (15°- 25°C; 59° - 77°F), to protect the study drug from light and to not freeze the study drug, as well as to instill one dose BID (preferably 8-12 hours apart) in the study eye on Days 0 to 83.

If deemed necessary by the investigator, study drug may also be instilled in the fellow eye. If the investigator deems that the fellow eye should also be treated, then the same unit-dose container used to dose the study eye should be used to deliver a dose to the fellow eye. If both eyes are treated with study drug, all study assessments will be performed on the treated eyes, but the fellow eye will only be analyzed for safety while the study eye will be analyzed for safety and efficacy.

During the dosing phase (Day 0 to Day 83), subjects will self-instill (or will have study drug instilled by the subject's caregiver) one drop of study drug BID on the study eye for 84 days. Subjects will then be followed for approximately 2 weeks during the evaluation phase (Day 84 to Day 98).

There will be 7 study visits for full study participation: 1 visit during the screening phase, 4 visits (Day 0, Day 7, Day 30, and Day 60) during the dosing phase, and 2 visits (Day 84 and Day 98) during the post-treatment evaluation phase.

Subjects' safety will be evaluated throughout the study. The safety parameters to be assessed are the incidence, severity, and relationship of adverse events (AEs) and serious adverse events (SAEs), discontinuations due to AEs, changes in visual acuity (VA) and intraocular pressure (IOP), and biomicroscopic and ophthalmoscopic findings in treated eyes.

Efficacy will be assessed as follows:

Primary efficacy endpoint: University of North Carolina Dry Eye Management Scale (UNC DEMS)

A reduction of 10% in patient-reported DED symptoms and reduction of impact of symptoms on daily life at Day 84 as defined by the UNC DEMS with SURF-100 as compared to vehicle, 0.05% cyclosporine ophthalmic emulsion, and 5% lifitegrast ophthalmic solution.

Secondary efficacy endpoints:

1. Tear Break-up Time (TBUT)

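### The AE triggers for a 3-line BCVA loss and a 10 mmHg IOP rise name only the study eye, although a fellow eye may be dosed and is then analysed for safety

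*Combined protocol and SAP*

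**What the plan says.** Section 9 (Adverse Events) has five examination-based reporting rules:

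| Rule | Condition | Eye named |
|---|---|---|
| BCVA | "A worsening of 3 lines or more in log of the minimum angle of resolution (logMAR) score in the study eye from baseline" or a prior visit | study eye |
| IOP change | "An increase from baseline or any prior study visit of 10 mmHg in IOP in the study eye should be captured" as an AE | study eye |
| IOP level | "An IOP of 30 mmHg or higher will be reported as an SAE" | none |
| Biomicroscopy | finding that is new or worse than before treatment | none |
| Ophthalmoscopy | "A new finding or a significant worsening (2 units or more) from baseline should be recorded as an AE" | none |

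Elsewhere the plan sets safety scope by treated eye. Section 2 states that, at the investigator's discretion, "study drug may also be instilled in the fellow eye", and that in this case "all study assessments will be performed on the treated eyes, but the fellow eye will only be analyzed for safety". Section 8 takes BCVA and IOP in treated eyes at Visits 3 to 7. The sight-threat criterion in the SAE definition of Section 9 also refers to treated eyes.

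Section 12.1 summarises AEs separately for study eye and fellow eye. It adds one ocular table that combines the eyes and counts each subject once per category.

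**The concern.** A dosed fellow eye receives the same drug and the same BCVA and IOP examinations as the study eye, but two of the five reporting rules do not reach it. A change that must be written up in one eye is left to judgment in the other. Nothing in the available text extends the two triggers to a dosed fellow eye.

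Two outputs are exposed. The fellow-eye AE summary can under-record these events relative to the study-eye summary, because the two are collected under different rules. In the combined ocular table, a subject whose only qualifying change is in the dosed fellow eye can be absent from the IOP or BCVA row. That subject is also absent from the count of subjects with any ocular AE if no other ocular AE is recorded.

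IOP is the more relevant of the two measures. Two of the seven arms contain betamethasone (SURF-100 and 0.01% BSP), and Section 6 lists raised IOP as a corticosteroid risk. Dosing of both eyes is also plausible: Section 4.1 requires a reported history of dry eye in both eyes, and Section 2 expects that both eyes of some subjects will qualify.

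**Working it through.** The plan gives no figure on this point to reproduce. The check is a comparison of texts, a bound for IOP, and an illustration with assumed inputs.

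**1. Which rules reach a dosed fellow eye**

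| Event | Study eye | Dosed fellow eye |
|---|---|---|
| BCVA loss of 3 lines or more | explicit AE | general AE definition only, or an SAE if a general SAE criterion is met |
| IOP rise of 10 mmHg, staying below 30 | explicit AE | general AE definition only, unless a general SAE criterion is met |
| IOP of 30 mmHg or higher | SAE | SAE, if the sentence is read as covering any eye |
| Biomicroscopy or ophthalmoscopy finding | explicit AE | explicit AE (no eye named) |

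The biomicroscopy and ophthalmoscopy rules also depend on change, but since they name no eye the gap does not extend to them.

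**2. Bound for IOP**

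Let r be the reference IOP (baseline or a prior visit). Read the trigger as a rise of at least 10 mmHg, and the 30 mmHg sentence as covering any eye. A rise that meets the trigger but stays below 30 needs r + 10 < 30, so r < 20 mmHg.

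- Example: 14 to 27 mmHg is a rise of 13 and stays below 30. It is an explicit AE in the study eye and not in the fellow eye.
- With r at 20 mmHg or more, a 10 mmHg rise reaches 30 and falls under the SAE sentence.

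BCVA has no absolute threshold, so no such bound exists.

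**3. Illustration of size (all inputs assumed)**

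- p: chance that an eye has a qualifying change, taken as equal for both eyes
- q: share of subjects with both eyes dosed
- c: chance that the second dosed eye also qualifies, given that one does
- j: chance that a fellow-eye-only change is recorded anyway
- o: chance that the subject has another recorded ocular AE, independent of the change

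Capture in the study eye is taken as complete.

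Subjects with a change in any dosed eye: p + q·p·(1 − c). Subjects with a change in the fellow eye only: q·p·(1 − c). The share missing from the specific row is

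R = (1 − j) · q(1 − c) / [1 + q(1 − c)]

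and p cancels. With c = 0.8, q(1 − c) is 0.05, 0.10 and 0.20:

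| j | q = 0.25 | q = 0.5 | q = 1 |
|---|---|---|---|
| 0 (upper bound) | 0.05/1.05 = 4.8% | 0.10/1.10 = 9.1% | 0.20/1.20 = 16.7% |
| 0.5 | 2.4% | 4.5% | 8.3% |
| 0.8 | 1.0% | 1.8% | 3.3% |
| 1 | 0% | 0% | 0% |

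The extreme case q = 1, c = 0.5, j = 0 gives 0.5/1.5 = 33%.

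For the count of subjects with any ocular AE, multiply by (1 − o). With o = 0.5, j = 0.5 and c = 0.8 the shares are 1.2%, 2.3% and 4.2%. For IOP, all these shares apply only to the rises described in step 2.

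**The case against.** The strongest reply is that Section 9 already imposes a duty to record. Its general AE definition has no eye restriction, and AEs found through study procedures must be recorded. BCVA and IOP in a treated fellow eye are such procedures. A serious loss of vision there can also be an SAE, because the sight-threat criterion covers treated eyes. This stands: what is missing is a numeric trigger, not a duty. But the general route depends on a judgment that the change is untoward, and Section 9 does not leave that judgment open for the study eye.

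Other points stand in part:

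- The values are still collected. BCVA and IOP are safety variables in Section 10.2, and Section 10.5 analyses the eyes separately as appropriate. This limits the harm but creates no AE record. The available text ends within the list of tables in Section 12.1, so nothing is inferred here about further per-eye summaries.
- Section 12.1 includes every reported fellow-eye AE and asks for caution with the combined table. Inclusion does not make a change reportable, and the caution concerns how fellow eyes are selected, not a different capture rule.
- No eye-versus-eye comparison is planned, and the same rule applies in every arm under masking. That is why no bias between arms is claimed.
- The 30 mmHg sentence follows a study-eye sentence and could be read as limited to that eye. The 20 mmHg bound depends on the wider reading; the narrower one would enlarge the gap.
- The illustration rests wholly on assumptions. It takes equal risk in both eyes, although Section 2 makes the worse eye the study eye when both qualify. It shows a range, not an estimate for this trial.

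**Conclusion.** The concern holds as a minor inconsistency. The scope of the BCVA and IOP change triggers (study eye) does not match the treated-eye scope that the plan uses for assessment, safety analysis and the sight-threat SAE criterion. Followed as written, the plan can under-ascertain these two events in dosed fellow eyes and, through them, in the combined ocular AE table.

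Confidence is high for the reading of the text. The size is unknown: it depends on how many fellow eyes are dosed and how often sites would record such changes anyway, and it is zero if they always do.

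**What to change.** Reconcile the eye scope of the two sentences in Section 9 (the 3-line BCVA worsening and the 10 mmHg IOP increase) with the treated-eye scope in Section 2, Section 8 and the SAE definition in Section 9. Leave the 3-line, 10 mmHg and 30 mmHg thresholds as they are. In the same edit, state which eyes the 30 mmHg sentence covers, since it names none.

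The cost is a wording change and a few more AE forms. No new measurement is needed, because BCVA and IOP are already taken in treated eyes at Visits 3 to 7.

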2. STUDY DESIGN

This study is a Phase 2, multicenter, randomized, double-masked, parallel-group clinical trial in subjects with dry eye disease (DED). Subjects 18 years of age and older with a diagnosis of dry eye disease who meet all study entry criteria will be enrolled. The investigator and his/her staff will not know which study medication the subject is receiving but will be able to determine this in the event of an emergency.

Prior to enrollment, the study will be discussed with prospective subjects and those wishing to enter will be asked to give written informed consent. Informed consent will be obtained prior to any study related procedures being performed. Once informed consent has been obtained, the subjects will be questioned regarding their medical history to determine whether or not they are in satisfactory health to enter the study and to determine if they meet the specific entry criteria.

During the screening period (Day -14 to Day 0) of the study, subject eligibility will be determined. All eligibility criteria must be met for randomization into the study. Subjects who meet all inclusion and none of the exclusion criteria at the Screening Visit may proceed directly to Visit 2 on Day 0 for randomization. Subjects who fail screening may be re-screened once and should repeat Screening Visit 1 (Day -14 to Day 0) within 30 days of the original screening visit. Approximately 280-350 subjects at approximately 40 investigational sites located in the United States who meet all study entry criteria will be randomized at Visit 2 (Day 0) in a balanced ratio to 1 of 7 treatment groups:

- SURF-100 (0.3% MPA/0.01% BSP)
- 0.1% MPA
- 0.3% MPA
- 0.01% BSP
- Vehicle
- 0.05% cyclosporine ophthalmic emulsion
- 5% lifitegrast ophthalmic solution

The study eye will be determined by the investigator based on the results of the ophthalmic examination. Some subjects may have both eyes qualify for the study. In these cases, data from the eye with the worst combined clinical signs and symptoms score at Visit 2 (Day 0), or at Visit 1 (Day -14 to Day 0) if Visit 2 is <5 days after Visit 1, will be identified as the study eye and will be analyzed for safety and efficacy throughout the study. If the total score is the same for both

eyes, the right eye will be designated as the study eye and data from the right eye will be analyzed for safety and efficacy.

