10.4. Data Handling: Handling of Missing Data

All missing data will generally not be imputed unless otherwise specified. For subjects who are withdrawn from the study prior to study completion, all data compiled up to the point of discontinuation will be used for analysis. All study discontinuations will be included in all analyses up to the time of study discontinuation. As per the protocol, an ITT analysis with the last-observation-carried-forward (LOCF) method will be conducted for the primary efficacy analysis.

For the classification of treatment emergent adverse events (TEAEs) and concomitant medications, the following will be applied in case of missing/incomplete dates:

- If all dates/times (start and stop) are missing, the event/medication will automatically be classified as a TEAE/concomitant medication.
- For AE/medication with a missing start date/time, if the event end date/time is prior to first study drug administration, the event will not be classified as a TEAE/concomitant medication.
- If only the AE start year/medication end year is present and is the same or is after the first study drug administration year unit, the event/medication will be classified as a TEAE/concomitant medication.
- If the AE start month and year/medication end month and year are present and are the same or after the first study drug administration month and year units, the event/medication will be classified as a TEAE/concomitant medication.

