12. SAFETY

12.1. Adverse Events

Adverse events will be summarized separately for those occurring in the study eye, in the fellow eye, and non-ocular events. For overall AE incidence summary, one table for ocular AEs (study eye and fellow eye combined) will be reported. In this table, each subject will be counted only once in each summary category, to avoid correlated data. However, the results should be interpreted with caution because fellow eyes are selective samples by study design. Regardless of whether the fellow eye is treated or not, all AEs reported for the fellow eye will be included for the safety analysis. AEs marked as 'Both Eyes (OU)' from the AE CRF page will be summarized both for study eye and fellow eye.

All AE verbatim terms will be coded using Medical Dictionary for Regulatory Activities (MedDRA) version 23.0 Update. Terms will be coded to the full MedDRA hierarchy, but the system organ class (SOC) and preferred term (PT) will be of primary interest for the analysis.

Treatment emergent adverse events (TEAEs) are defined as AEs that first occurred or worsened on or after the date of first administration of study drug. If missing dates or time prevent a clear determination as to whether the AE is treatment emergent, the AE will be regarded as a TEAE.

While all AEs will be summarized, the main AE summaries will be restricted to TEAEs only. Treatment emergent adverse events will be summarized descriptively. For the summary of TEAEs, if a subject experienced the same AE multiple times, this will only be counted once for the purpose of counting the number of patients experiencing that AE. Summary tables will include the number of subjects (%) experiencing an AE and the number of AEs.

The TEAE summaries will include:

- Overall Summary of Subjects with at Least One Adverse Event
- Summary of TEAEs by SOC and PT
- Summary of TEAEs with an Incidence $\geq 5\%$ by SOC and PT
- Summary of Serious TEAEs by SOC and PT

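### Section 12.1 cuts treatment-emergent AEs at the date of first dose, so AEs that arise before dosing on Day 0 are counted as TEAEs

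*Combined protocol and SAP*

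**What the plan says.** Section 12.1 defines TEAEs as "AEs that first occurred or worsened on or after the date of first administration of study drug" and limits the main AE summaries to them, including a table of terms at 5% or more and a table of serious TEAEs. Its next sentence makes an AE a TEAE by default when a missing date or time prevents classification.

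Section 10.6 takes baseline as the last non-missing value before the time of first dosing, and states that the first dosing day is Day 0. Section 10.4, for an AE with no start recorded, compares the end date and time with first administration. It adds: "If all dates/times (start and stop) are missing, the event/medication will automatically be classified as a TEAE/concomitant medication".

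Section 8 schedules slit lamp, BCVA and IOP at Visit 2 before randomization, and only if Visit 2 is more than 5 days after Visit 1. In Section 2 the Visit 1 window runs up to Day 0, and eligible subjects may go straight on to Visit 2.

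Section 9 opens AE collection early: "The AE reporting period for this trial begins upon signing the ICF". A BCVA loss of 3 lines or an IOP rise of 10 mmHg in the study eye is an AE when compared with baseline or with any earlier visit. For biomicroscopy, "Any biomicroscopy observations noted prior to Screening (Visit 1) should be recorded as ocular medical history", and treatment-emergent findings are "findings that were not present prior to treatment or a worsening relative to the pretreatment baseline".

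**The concern.** Three sections draw the line between before and after treatment in different places. Section 10.6 draws it at the dosing time. Section 9, for biomicroscopy, draws it at the start of treatment. Section 12.1 draws it at the start of the calendar day of first dosing. On Day 0 these differ, and Day 0 is when pre-dose examinations take place.

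The main safety tables would then contain events that the drug cannot have caused. This matters somewhat more than usual here, because Section 6 says that adverse reactions to topical ophthalmic mycophenolic acid have not yet been investigated, so readers will look at absolute TEAE rates as well as differences between arms.

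The biomicroscopy rule has a related recording gap. The first study slit lamp is at Visit 1, after consent ("Informed consent will be obtained prior to any study related procedures being performed"). A finding first seen there was not noted before Screening and is not treatment-emergent. Section 9 does not say where it goes, and about 40 sites would have to decide for themselves.

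**Working it through.** The plan states no figure on this point, so the check is to follow pre-dose events through the rules and then size one misclassified subject.

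**Following the rules**

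1. *IOP or BCVA change.* Suppose Visit 1 is on Day -10 and Visit 2 on Day 0. The gap exceeds 5 days, so the examinations are repeated before randomization. Study-eye IOP has risen by 10 mmHg since Visit 1. Section 9 makes this an AE, because the comparator may be any earlier visit. Section 10.6 makes the same reading the baseline value. Section 12.1 makes the AE a TEAE, because its start date is the date of first dosing. One pre-drug reading is both the baseline and a treatment-emergent event.
2. *IOP level.* Section 9 also makes any IOP of 30 mmHg or higher an SAE, with no comparator. A reading that first reaches that level at pre-dose Visit 2 would enter the serious TEAE table.
3. *Reaction to a pre-dose test.* Inclusion criterion 7 requires the anesthetized Schirmer test at Visit 2 when the gap exceeds 5 days, so it precedes randomization. An AE from the anesthetic or the strip, dated Day 0, is a TEAE. The same holds for a Visit 1 held on Day 0.
4. *New slit-lamp finding at pre-dose Visit 2.* Under Section 9 it was present before treatment and is not treatment-emergent. If it is entered as an AE with a Day 0 start, Section 12.1 makes it a TEAE.
5. *Same event, less complete record.* If the start is missing but the end time precedes the first dose, Section 10.4 says it is not a TEAE. With the Day 0 start recorded, Section 12.1 says it is. The better-documented event gets the worse classification.
6. *No Day 0 examination.* If Visit 1 is before Day 0 and Visit 2 follows by 5 days or fewer, none of these examinations is scheduled on Day 0, and they do not raise the problem.
7. *Visit 1 slit-lamp finding before Day 0.* Section 9 gives it no stated place. If it is entered as an AE with a full start date before Day 0, it is not a TEAE.

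**Size of one subject** (assuming equal arms, all dosed)

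- Arm size, from the 280 to 350 subjects and 7 groups in Section 2: 280/7 = 40; 350/7 = 50.
- One subject: 1/40 = 2.5 percentage points; 1/50 = 2.0.
- To reach the 5% table, the same term is needed in 2/40 = 5.0% of an arm, or in 3/50 = 6.0% (2/50 = 4.0% falls short).

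**Effect on arm differences.** Let p be an arm's true any-TEAE risk and q the chance of a pre-dose Day 0 AE, the same in every arm and independent of later events. The reported risk is 1 - (1 - p)(1 - q) = p + q - pq. The difference between arms A and B becomes (pA - pB)(1 - q). The documents give no value for q. Purely as an assumed range, q = 1% to 5% multiplies the difference by 0.99 to 0.95.

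**The case against.** The strongest reply is that this is minor. Misclassified events precede treatment, so no arm is favored in expectation. A date rule errs toward counting events, which is the cautious direction for safety. The Day 0 case needs a long enough screening interval or a same-day Visit 1. All of that stands, and it limits the size of the point.

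It can also be said that 12.1 has time in mind, since its fallback sentence mentions missing times. But that sentence acts only when information is missing, and it then defaults to TEAE. It does nothing for an AE with a recorded Day 0 date. Nor does the AE definition in Section 9, which refers to use of a study drug, dispose of the matter. The AE period starts at consent, and the BCVA and IOP rules expressly allow a pre-dose comparator.

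A reader might infer something stronger: that long-standing slit-lamp findings first seen at Visit 1 must go on the AE form and then become TEAEs through the missing-date rule. The documents do not support this.

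- The recording duty ("noted as a result of procedures carried out on the subject, during the AE-reporting period must be recorded by site staff") has AEs as its subject, not every observation.
- The biomicroscopy rule sends only treatment-emergent findings to the AE form.
- The pre-existing exemption covers "a disorder present before the AE-reporting period started and noted on the Systemic and/or Ocular Medical History Forms" and sets no deadline for the note. Section 2 has history taken after consent, so an older disorder can still be entered and exempted.
- The missing-date rule would bite only if such a finding were entered as an AE with no date at all, although its examination date is known.

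The documents give no frequency for such findings, and exclusion criterion 4 removes many ocular conditions.

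**Conclusion.** The inconsistency on Day 0 is real and follows from the plain wording. An AE that starts before the first dose on that day is a TEAE under 12.1, although 10.6 places the same observation before treatment and, for biomicroscopy, Section 9 does not call it treatment-emergent. It is limited to subjects with a pre-dose examination or pre-dose AE on Day 0.

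The consequence is a slight inflation of TEAE counts in all seven arms and a slight dilution of differences. The number of subjects affected cannot be derived from the documents. The absence of bias toward any arm rests on these events preceding treatment, which makes them independent of assignment in expectation; chance imbalance remains possible in arms of 40 to 50. Efficacy is unaffected.

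The biomicroscopy sentence leaves Visit 1 findings unassigned. That is a gap in recording instructions; it does not by itself create AEs or TEAEs.

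**What to change.** **Section 12.1.** Define TEAEs by the date and time of first dose. AEs that start before the first dose on Day 0, including those found at pre-randomization examinations, are reported as AEs but not as TEAEs. If they worsen after the first dose they count as TEAEs, as the present wording already provides. Where the Day 0 time is unknown and no pre-dose examination documented the event, keep the conservative TEAE default.

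**Section 9, biomicroscopy.** State that findings already present at the Visit 1 examination are recorded as ocular history, and that findings newly arising after consent but before dosing are recorded as non-treatment-emergent AEs. It would be wrong to send everything seen at pre-dose Visit 2 to history. That would remove genuine post-consent events, such as an injury from the Visit 1 Schirmer strip, from AE reporting, and would contradict the consent-based AE period.

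**Cost.** A few sentences, plus an onset time for Day 0 AEs. Section 8 already has dose times recorded in the dosing diary, and Section 10.4 already refers to event times, but the documents do not show whether the AE form collects onset time. TEAE counts will be slightly lower than under the date rule.
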